5.9.6.2 Pharmacokinetics

C_{max} and AUC are the primary PK parameters of interest in PK similarity studies with a subcutaneous drug administration. These and additional PK parameters will be determined for each subject using non-compartmental methods. All parameters will be reported with standard descriptive statistics including the geometric mean and coefficient

of variation. Calculation of PK parameters will be performed using actual sampling times.

5.9.7 Additional Analyses

5.9.7.1 Proteomics and small RNA Transcriptomics Analysis

A combination of differential expression testing of signals analysis, and clustering techniques will be used demonstrate subject response to each product. Differentially expressed plasma proteins and small RNAs will be identified using a 10% false discovery rate. Following technical and independent validation of the most promising or top 1% biomarker(s), dose- and exposure-response analysis will be performed as described above for the primary biomarker(s). The AUEC change along with maximal effect at a single time point for a promising biomarker(s) will also be calculated. The values, variability and characteristics of the proteomic-array-based biomarkers will be compared to the traditional biomarker analysis outlined above. Based on proteomic and small RNA transcriptomic findings, the potential for a composite of relevant biomarkers to demonstrate PD similarity will also be evaluated. Additional details regarding the statistical methods for the proteomic and small RNA transcriptomic analyses will be described in a separate protocol.

5.9.7.2 Genomic Analysis

Genetic variation may contribute to the PK or PD response to a drug. Analyses of buffy coat DNA may include genome-wide studies, including (but not limited to) to the generation of variant data and/or genomic sequencing in hypothesis-generating studies. Additional details regarding the statistical methods for the genomic analyses will be described in a separate protocol.

5.9.7.3 Other Omic Analyses

Epigenetic variation such as DNA methylation has the capacity to contribute to the PD or PK response to a drug. Moreover, profiling metabolites in biofluids may have utility in the identification of circulating PD biomarkers. The generation of additional omics profiles (e.g., metabolomics and methylomics) from an alternative biospecimen such as urine can inform on the utility of these technologies for PD biomarker identification and the analytical framework required for future studies involving this biospecimen. These analyses may also inform on biofluid specificity. These analyses will be considered hypothesis-generating. Additional details regarding the statistical methods for the omics analyses will be described in a separate protocol.

5.9.8 Safety Analyses

5.9.8.1 Adverse Events

All AEs will be coded using the latest version of the Medical Dictionary for Regulatory Activities. The incidence of TEAEs, organized by system organ class and frequency, will be summarized by seriousness, severity, relationship to treatment, and by treatment at onset of the TEAE. A detailed listing of serious AEs and TEAEs leading to withdrawal will also be provided.

5.9.8.2 Clinical Laboratory Tests

Clinical laboratory results (hematology, serum chemistry, and urinalysis) will be summarized using descriptive statistics (number of subjects, mean, SD, minimum, median, and maximum). Clinical laboratory results will be classified as normal or abnormal, according to the reference ranges of the individual parameter. The number and percentage of subjects with abnormal laboratory results will be provided. No statistical testing will be performed on clinical laboratory data.

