5.2.1 Inclusion Criteria

Subjects who meet all of the following inclusion criteria will be eligible to participate in the study:

- 1. Subject signs an IRB approved written informed consent and privacy language as per national regulations (e.g., Health Insurance Portability and Accountability Act authorization) before any study related procedures are performed.
- 2. Subject is a healthy man or woman, 18 to 55 years of age, inclusive, who has a body mass index of 18.5 to 32.0 kg/m², inclusive, at Screening.
- 3. Subject has a LDL-C level >=100 and <=190 mg/dL inclusive, at Screening.

- 4. Subject has normal medical history findings, clinical laboratory results, vital sign measurements, 12 lead electrocardiogram (ECG) results, and physical examination findings at Screening or, if abnormal, the abnormality is not considered clinically significant (as determined and documented by the investigator or designee).
- 5. Subject must have a negative test result for alcohol and drugs of abuse at screening and Check-in (Day -1).
- 6. Female subjects must be of non-childbearing potential or, if they are of childbearing potential, they must: 1) have been strictly abstinent for 1 month before Check in (Day -1) and agree to remain strictly abstinent for the duration of the study and for at least 1 month after the last application of study drug; OR 2) be practicing 2 highly effective methods of birth control (as determined by the investigator or designee; one of the methods must be a barrier technique) from at least 1 month before Check in (Day -1) until at least 1 month after the last application of study drug.
- 7. Male subjects must agree to practice 1 highly effective method of birth control (as determined by the investigator or designee) from at least 1 month before Check in (Day-1) until at least 1 month after the last application of study drug.
- 8. Subject is highly likely (as determined by the investigator) to comply with the protocol defined procedures and to complete the study

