5.2.2 Exclusion Criteria

Subjects who meet any of the following exclusion criteria will not be eligible to participate in the study:

- 1. Subject is taking cholesterol medication (e.g. statins).
- 2. Subject is anemic (i.e., with Hct or Hgb less than the lower limit of normal) or has any chronic condition(s) that may impact blood sample collection.
- 3. Subject has had previous exposure to the biologic Evolocumab or Alirocumab.
- 4. Subject has a history of asthma.
- 5. Subject has a history of anaphylaxis from environmental exposures such as peanuts or bee stings.
- 6. Subject has an allergic history that includes urticaria, angioedema or respiratory coughing or difficulty breathing.
- 7. Subject has a history of severe local reactions or generalized erythema from skin allergen testing.
- 8. Subject has used any prescription or nonprescription drugs (including aspirin or NSAIDs and excluding oral contraceptives and acetaminophen) within 14 days or 5 half-lives (whichever is longer) or complementary and alternative medicines within 28 days before the first dose of study drug.
- 9. Subjects are currently participating in another clinical study of an investigational drug or are have been treated with any investigational drug within 30 days or 5 half-lives (whichever is longer) of the compound.

11

- 10. Subject has used nicotine-containing products (e.g., cigarettes, cigars, chewing tobacco, snuff) within 6 weeks of Screening.
- 11. Subject has consumed alcohol, xanthine-containing products (e.g., tea, coffee, chocolate, cola), caffeine, grapefruit, or grapefruit juice within 48 hours of dosing. Subjects must refrain from ingesting these throughout the study.
- 12. Subject has any underlying disease or surgical or medical condition (e.g., cancer, human immunodeficiency virus [HIV], severe hepatic or renal impairment) that could put the subject at risk or would normally prevent participation in a clinical study. This includes subjects with any underlying medical conditions that put subjects at higher risk for coronavirus disease of 2019 (COVID-19) complications; per current Center for Disease Control and Prevention (CDC) recommendations this includes:
 - People with chronic lung disease or moderate to severe asthma
 - People who have serious heart conditions
 - People who are immunocompromised

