 - Many conditions can cause a person to be immunocompromised, including cancer treatment, smoking, bone marrow or organ transplantation, immune deficiencies, poorly controlled HIV, and prolonged use of corticosteroids and other immune weakening medications
 - People with severe obesity (body mass index of 40 or higher)
 - People with diabetes
 - People with chronic kidney disease undergoing dialysis
 - People with liver disease
- 13. Subject has any signs or symptoms that are consistent with COVID-19. Per current CDC recommendations this includes subjects with the symptoms cough or shortness of breath or difficulty breathing, or at least two of the following symptoms: fever, chills, repeated shaking with chills, muscle pain, headache, sore throat or new loss of taste/smell. In addition, the subject has any other findings suggestive of COVID-19 risk in the opinion of the investigator.
- 14. Subject tests positive for severe acute respiratory syndrome coronavirus 2 (SARS-CoV-2) by a molecular diagnostic test performed prior to admission.
- 15. Subject has known or suspected allergies or sensitivities to any study drug.
- 16. Subject has clinical laboratory test results (hematology, serum chemistry lipid panel and comprehensive metabolic panel) at Screening that are outside the reference ranges provided by the clinical laboratory and considered clinically significant by the investigator.
- 17. Subject has a positive test result at Screening for HIV 1 or 2 antibody, hepatitis C virus load, hepatitis C virus antibodies, or hepatitis B surface antigen.
- 18. Subject is unable or unwilling to undergo multiple venipunctures for blood sample collection because of poor tolerability or poor venous access.
- 19. Female subjects are pregnant or lactating before enrollment in the study.

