5.6.3.1 Check-in

The following procedures and assessments will be performed at Check-in (Day -1):

- Perform/review results from SARS-CoV-2 molecular diagnostic test
- Review inclusion/exclusion criteria to confirm subject eligibility
- Review medical history
- Perform alcohol and drug screening (amphetamines, barbiturates, benzodiazepines, cannabinoids, cocaine, alcohol, opiates, phencyclidine, propoxyphene, and methadone)
- Perform a serum pregnancy test (female subjects only)
- Admit subject to the study clinic
- Randomization (after completion of check-in procedures on Day -1 or just before dosing on Day 1)
- Record concomitant medications
- Monitor for AEs
- Perform clinical laboratory tests (hematology, serum chemistry, and urinalysis)
- Measure vital signs (blood pressure, heart rate, respiratory rate, and oral body temperature)
- Perform a safety 12-lead ECG
- Perform a comprehensive physical examination
- Collect whole blood for LDL-C and ApoB quantitation (5 mL)
- Collect whole blood (5 mL) and process for plasma for proteomic and small-RNA transcriptomic analyses
- Collect urine (3-5 mL) for omic analysis (e.g., transcriptomics and/or metabolomics)

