5.9.8.3 Vital Sign Measurements

Vital sign measurements and changes from baseline will be summarized using descriptive statistics (number of subjects, mean, SD, minimum, median, and maximum) by treatment and time point.

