5.9.8.4 Safety 12-lead Electrocardiograms

Safety 12-lead ECG data and changes from baseline will be summarized using descriptive statistics (number of subjects, mean, SD, minimum, median, and maximum) by treatment and time point. The extent of change in each of the treatments will also be compared. The incidence of pathological ECG interpretive statements at Baseline and during treatment will be assessed among the treatments.

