7.7.2 Clinical Laboratory Tests

Clinical laboratory results (hematology, serum chemistry, and urinalysis) will be summarized using descriptive statistics (number of subjects, mean, SD, minimum, median, and maximum). Clinical laboratory results will be classified as normal or abnormal, according to the reference ranges of the individual parameter. No statistical testing will be performed on clinical laboratory data.

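### Laboratory results are not referenced to baseline or split by direction in the protocol or the SAP, so the protocol's count of abnormal subjects mixes pre-existing with new abnormalities

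*Protocol*

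**What the plan says.** Protocol 5.9.8.2 plans numeric summaries of hematology, chemistry and urinalysis, a two-category classification against the reference range, and this count: "The number and percentage of subjects with abnormal laboratory results will be provided". It names no baseline, visit, treatment arm or direction for any of them.

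SAP 7.7.2 repeats the numeric summaries and the classification: "Clinical laboratory results will be classified as normal or abnormal, according to the reference ranges of the individual parameter". The count is absent, and neither change from baseline nor direction is added.

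The entry criteria let out-of-range values in. Inclusion 4 accepts an abnormal screening result "if abnormal, the abnormality is not considered clinically significant (as determined and documented by the investigator or designee"). Exclusion 16 removes only results that are "outside the reference ranges provided by the clinical laboratory and considered clinically significant by the investigator". Exclusion 2 is stricter for one direction of two parameters: "Subject is anemic (i.e., with Hct or Hgb less than the lower limit of normal").

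Other safety data are referenced to baseline. Protocol 5.9.8.3: "Vital sign measurements and changes from baseline will be summarized using descriptive statistics", by treatment and time point. Protocol 5.9.8.4, which also plans ECG changes from baseline: "The incidence of pathological ECG interpretive statements at Baseline and during treatment will be assessed among the treatments". SAP 7.7.3 and 7.7.4 keep a baseline reference for both.

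A laboratory baseline will exist. Protocol 5.6.3.1 has the site "Perform clinical laboratory tests (hematology, serum chemistry, and urinalysis") on Day -1, and Table 9-1 labels that column check-in/baseline.

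**The concern.** A count of subjects with an abnormal result is useful in a safety report if it indicates what changed after dosing. As worded, it does not separate three kinds of subject: one who entered out of range and stayed there, one who moved out of range after dosing, and one who crossed from one side of the range to the other. A low and a high result count alike.

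With 8 subjects per arm, one subject is 1/8 = 12.5 percentage points. A chance imbalance in who entered with a harmless out-of-range value can therefore create or hide a visible arm difference. Direction matters for parameters such as glucose: protocol 5.1.3 lists diabetes mellitus among the common evolocumab reactions, and only a high value would bear on that.

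This is separate from the protocol and SAP disagreeing on whether the count is produced. Restoring it to the SAP in its present wording would bring the same weakness back.

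**Working it through.** The plan states no figure for this summary, so there is none to reproduce. The defect follows from the text; the arithmetic only sizes it.

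**Text comparison**

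| Safety data | Baseline reference | Direction | Treatment and time point stated |
|---|---|---|---|
| Laboratory, protocol 5.9.8.2 | none | none | no |
| Laboratory, SAP 7.7.2 | none | none | no |
| Vital signs, protocol 5.9.8.3 and SAP 7.7.3 | change from baseline | numeric change | yes |
| ECG, protocol 5.9.8.4 | change from baseline; findings at baseline and during treatment | numeric change | yes, for the numeric data |

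**Inputs for the size**

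- From Table 9-1: chemistry and hematology at screening, check-in, 24 h, Day 7, Day 28 and end of study. That is two pre-dose and four post-dose draws. Urinalysis has fewer and is not modelled.
- From protocol Table 5-1: 8 subjects per arm.
- Assumed, not in the documents: the reference range is a central 95% interval, values are normal on a suitable scale, the between-subject share of variance r is 0.5 to 0.85, there is no drug effect, and there is no selection at entry.

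**Formulas.** Let subject i have z = sqrt(r)·b + sqrt(1-r)·e at each draw, with b and e independent standard normal, and flag |z| > 1.96. Given b, one draw is in range with probability

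p(b) = Φ((1.96 - sqrt(r)·b)/sqrt(1-r)) - Φ((-1.96 - sqrt(r)·b)/sqrt(1-r)).

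Averaging over b:

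- flagged at any of four post-dose draws: P1 = 1 - E[p^4]
- flagged post-dose and abnormal at check-in: P2 = E[(1-p)(1-p^4)]
- flagged post-dose and abnormal at screening or check-in: P3 = E[(1-p^2)(1-p^4)]

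**Results, per parameter, by numerical integration**

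| r | P1 | P2 | P2/P1 | P3 | P3/P1 |
|---|---|---|---|---|---|
| 0.50 | 15.6% | 2.3% | 15% | 3.9% | 25% |
| 0.70 | 13.0% | 3.2% | 25% | 5.0% | 38% |
| 0.85 | 10.5% | 3.9% | 38% | 5.5% | 52% |

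P2/P1 is the share that a check-in-based definition of newly abnormal would remove from a post-dose count.

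Per arm of 8, the expected number flagged post-dose on one parameter is 8 × 0.105 = 0.8 to 8 × 0.156 = 1.2 subjects. Of these, 8 × 0.023 = 0.2 to 8 × 0.039 = 0.3 were already abnormal at check-in.

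**The case against.** The strongest reply is that the count may never be produced. The SAP drops it, and if the SAP governs, only the lack of a baseline reference and of direction remains live. That stands, and it is why the point covers both documents and not the count alone.

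The second reply is that other outputs carry a laboratory signal. The adverse event definition (protocol 5.7.4.1.1) includes abnormal laboratory findings. Treatment-emergent events must begin after dosing and are tabulated by treatment (5.9.8.1). Out-of-range values are reviewed for clinical significance (5.7.4.2), numeric results are summarized, and all data are listed. This also stands, in part. The adverse event route depends on case-by-case judgment, the numeric summaries are not tied to baseline or visit, and listings give no summary by arm. A reader might infer that the plan cannot show any laboratory effect of the drugs; these routes mean the documents do not support that.

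A reader might also infer that about half of the flagged subjects would be pre-existing cases. Under the same assumptions that figure (44% to 60%) appears only if all six draws are pooled into one flag and an abnormal value at either screening or check-in counts as prior. The protocol does not say that visits are pooled; a table by visit would show check-in separately. Nor should flags be added up across parameters, since the classification is by individual parameter.

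Finally, a shift table can be set in table shells, and at 8 per arm it will be sparse. Both are true, and they bear on priority only.

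**Conclusion.** The point holds and is minor. From the text alone: neither document references laboratory results to baseline or separates low from high, the entry criteria admit non-significant out-of-range values (low hematocrit or hemoglobin excepted), and the protocol's count therefore mixes pre-existing with new abnormalities.

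Its size rests on assumed inputs. With central 95% ranges, a between-subject variance share of 0.5 to 0.85 and no drug effect, about 15% to 38% of subjects flagged after dosing would already be abnormal at check-in, or 25% to 52% at screening or check-in. Removing subjects with clinically significant screening values, which the calculation ignores, would tend to lower these shares; more stable parameters push them up.

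This is a descriptive safety summary in a single-dose pilot. No primary or secondary endpoint depends on it.

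**What to change.** Use the same wording in protocol 5.9.8.2 and SAP 7.7.2, replacing the plain count:

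1. A shift table by treatment and parameter: low, normal or high at check-in against the lowest and the highest post-dose result. For categorical urinalysis items, use normal or abnormal.
2. The number and percentage of newly abnormal subjects, low and high separately, counting only subjects in range at check-in, with that number as the denominator.
3. Change from check-in by treatment and time point, as already planned for vital signs.

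State that check-in is the laboratory baseline, and what is used if that sample is missing.

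The data are already scheduled, so the cost is wording and standard programming. The downside is a slightly longer table set with many small cells: at 8 per arm, one subject is still at least 12.5 percentage points.

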5.9.8.3 Vital Sign Measurements

Vital sign measurements and changes from baseline will be summarized using descriptive statistics (number of subjects, mean, SD, minimum, median, and maximum) by treatment and time point.

5.9.8.4 Safety 12-lead Electrocardiograms

Safety 12-lead ECG data and changes from baseline will be summarized using descriptive statistics (number of subjects, mean, SD, minimum, median, and maximum) by treatment and time point. The extent of change in each of the treatments will also be compared. The incidence of pathological ECG interpretive statements at Baseline and during treatment will be assessed among the treatments.

5.9.8.5 Physical Examinations

Physical examination findings will be presented in a data listing, and abnormal physical examination findings will be recorded as AEs.

5.9.8.6 Other Safety Data

All concomitant medication usage and medications that changed in daily dose, frequency, or both since the subject provided informed consent will be summarized for each subject.

5.9.9 Interim Analyses

No interim analyses are planned.

5.9.10 Missing Data

Missing data will not be imputed. Data that are excluded from the descriptive or inferential analyses will be included in the subject data listings. This will include data from subjects not in the particular analysis population, measurements from unscheduled visits, or extra measurements that may arise from 2 or more analyses of the biofluid sample at the same time point.

5.10. Data Quality Assurance

Completed eCRFs are required for each subject randomly assigned to study drug. Electronic data entry will be accomplished through the ClinSpark® remote electronic data capture system, which allows for on-site data entry and data management. This system provides immediate, direct data transfer to the database, as well as immediate detection of discrepancies, enabling site coordinators to resolve and manage discrepancies in a timely manner. Each person involved with the study will have an individual identification code and password that allows for record traceability. Thus, the system, and subsequently any investigative reviews, can identify coordinators, investigators, and individuals who have entered or modified records.

Furthermore, the investigator retains full responsibility for the accuracy and authenticity of all data entered into the electronic data capture system. The completed dataset and their associated files are the sole property of the sponsor and should not be made available in any form to third parties, except for appropriate governmental health or regulatory authorities, without written permission of the sponsor.

6. Ethical Considerations

6.1. Ethical Conduct of the Study

This study will be performed in accordance with the recommendations guiding physicians in biomedical research involving human subjects adopted by the 18th World Medical Association General Assembly, Helsinki, Finland, 1964 and later revisions, as well as, United States Title 45 Code of Federal Regulations (CFR) Part 46 GCP, and International Council for Harmonisation (ICH) guidelines describing technical requirements for registration of pharmaceuticals for human use.

